7.2 Imputation of AF/ AFL/AT Freedom

Subjects who were randomized and received study procedure but have no post-treatment assessments will be conservatively imputed as having failed to achieve freedom from AF/ AFL/AT (e.g., treatment failure). Similarly, subjects who were randomized and received study procedure but do not have treatment assessments following the 3-month blanking period (as described in Section 7.4.2), or a visit was performed but insufficient information was collected to determine whether or not AF/AFL/AT was experienced and/or whether Class I/III AADs were administered, will also be imputed as treatment failures. Subjects who do not have complete information for the efficacy evaluation period (for example, withdrew before 12 months) but have sufficient information to conclude that they would be classified as *not* AF/AFL/AT free (such as: new or increased dose of Class I/III AAD or documented findings of AF/AFL/AT) will be considered treatment failures. These subjects will *not* be considered to have been imputed, for the purpose of tipping point or multiple imputation analyses, as it is clear that they would have been treatment failures even if complete information had been collected.

The same approach will be utilized to impute AF freedom for secondary efficacy analyses.

A tipping-point analysis will also be performed, as described in Section 9.3.2, which will be performed on un-imputed data. Further details on criteria for treatment failure are provided in study protocol Section 1.5.

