- Similarly, the 12 month post-procedure visit (as defined for the end of the efficacy evaluation period) will be determined as follows. If the subject's 12 month visit is within the visit window specified in Section 3.2 (365 days \pm 30 days), the day of the 12 month visit will be used. If the nominal 12 month visit is not performed but an unscheduled visit falls within that visit window and is categorized as the 12 month visit per Section 7.3, the day of that visit will be used. If multiple unscheduled visits fall within that window (and there is no nominal 12 month visit), the unscheduled visit closest (with sufficient efficacy data to determine if a subject was AT/AF/AFL free) to the 365 day mark will be considered the 12 month post-procedure visit for this purpose. If a subject does not have a visit within the 12 month window, but has subsequent study visits or other criteria such that it is necessary to define a date for the hypothetical 12 month visit, the 365th day after the study procedure will be used.
- If necessary, the 1 month visit, 6 month visit and 18 month long-term follow-up visit date will be defined as necessary for efficacy purposes using the approach spelled out for the 12 month visit.

7.4.3 **Anti-Arrhythmic Drugs**

Class I/III AADs will include Quinidine, Procainamide, Disopyramide, Lidocaine, Phenytoin, Mexiletine, Tocainide, Flecainide, Propafenone, and Moricizine (Class I AADs) as well as Amiodarone, Sotalol, Ibutilide, Dofetilide, Dronedarone, and E-4031 (Class III AADs). Prior to database lock, a list of all medications (both prior and concomitant) taken by subjects who have received a study procedure will be provided to the Medical Monitor or designee for review. This list will not include subject identifiers or treatment arm. The Medical Monitor or designee will indicate which medications should be categorized as Class I or III AADs. This information will be finalized prior to database lock and subsequent unblinding of study sponsor, and incorporated into analysis datasets. If desired, a list of previously failed Class I/III AADs as recorded at the Baseline visit may also be provided to the monitor or designee for reference.

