- 11) Freedom from AF/AFL/AT requiring intervention (emergency visits, cardioversion, urgent care visit, re-ablation, etc.), data permitting.
- 12) Achievement of $\geq 75\%$ reduction in baseline AF burden at 12 months post-procedure, where subjects with new or increased dosage of Class I/III AADs during the efficacy evaluation period are categorized as not achieving $\geq 75\%$ reduction, using the Fisher's Exact test as described in Section 9.4.1.
- 13) Achievement of no more than 12% AF burden at 12 months post-procedure, where subjects with new or increased dosage of Class I/III AADs during the efficacy evaluation period are categorized as not achieving $\leq 12\%$ AF burden, using the Fisher's Exact test as described in Section 9.4.1.
- 14) Freedom from stroke-relevant AF/ AFL/AT-duration (cutoff of 1 hour), data permitting.
- 15) Regression of AF: conversion of persistent to paroxysmal AF, data permitting.
- 16) Prevention in AF progression: time to first episode of persistent AF, data permitting.

Multiplicity tests #1-16 are based on the 12 month data analyses, and will be performed at that time. The following multiplicity tests are based on data collected at the 18 month visit. Therefore, they will be performed after data collection and cleaning is completed for the 18 month visit. As described above, these endpoints will only be evaluated using the fixed-sequence procedure if all of the prior endpoints are significant.

- 17) Success or failure to achieve a 90% reduction from baseline AF burden with and without Class I/III AADs at 18 months post-procedure, where subjects with new or increased dosage of Class I/III AADs during the efficacy evaluation period are categorized as not achieving $\geq 90\%$ reduction, as described in Section 9.5.1.
- 18) Change in number of hospitalizations for the 12 months post-procedure period (6 months to 18 months post- procedure) compared to the number of hospitalizations in the 12 months prior to the procedure, as described in Section 9.5.4, date permitting.
- 19) Change in rhythm disturbance treatments (e.g. electrical or pharmacological cardioversion, AAD therapy, supraventricular ablative therapy) 12 months post-procedure period (6 to 18 months post-procedure) compared to 12 months prior to the procedure, as described in Section 9.5.5, data permitting.

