9.4 Secondary Efficacy Analysis

All secondary analyses will be performed on the ITT population. These analyses may be repeated on the mITT and PP populations.

9.4.1 $\geq 90\%$ Reduction in AF Burden

The AF burden, as a percentage, is recorded on the Holter Monitor eCRF. The recorded values and percent change from baseline in AF burden will be summarized by time point at 6, 12, and 18 months post-procedure.

The percent change from baseline at 12 months will be categorized as $\geq 90\%$ reduction (percent change $\leq -90\%$) or $< 90\%$ reduction (percent change $> -90\%$). The proportion of subjects achieving $\geq 90\%$ reduction at 12 months will be compared between treatment arms using Fisher's Exact test.

This analysis will be repeated for the following subsets of subjects:

- Subjects who have taken a Class I/III AAD during the efficacy evaluation period (excluding previously failed Class I/III AADs with no increase in dosage).

- Subjects who have *not* taken a Class I/III AAD during the efficacy evaluation period (excluding previously failed Class I/III AADs with no increase in dosage).
- Subjects who have taken any Class I/III AAD during the efficacy evaluation period.

No imputation will be performed for missing data.

These analysis (on all subjects and the three subsets) will also be repeated where subjects with a new or increased dosage of Class I/III AADs during the efficacy evaluation period will be categorized as not having achieved $\geq 90\%$ reduction. This will be performed on the ITT population. No imputation will be performed for missing data.

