9.5 Exploratory Efficacy Analysis

9.5.1 Reduction from Baseline AF Burden at 18 Months

The reduction in AF burden from baseline to 18 months will be categorized and analyzed as described for the reduction in AF burden at 12 months (Section 9.4.1).

This analysis will be performed on the ITT population. No imputation will be performed for missing data.

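### Test 17 reads AF burden at 18 months but checks for new or increased AADs only up to the 12-month visit, leaving about 185 days of drug starts uncounted

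*SAP*

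**What the plan says.** SAP 9.2 places the 18-month burden endpoint at position 17: "Success or failure to achieve a 90% reduction from baseline AF burden with and without Class I/III AADs at 18 months post-procedure". The same item then adds a failure rule, "where subjects with new or increased dosage of Class I/III AADs during the efficacy evaluation period are categorized as not achieving" the required reduction.

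The period named in that rule has no free-standing definition, but its end is fixed in two places. SAP 7.4.2 says "the 12 month post-procedure visit (as defined for the end of the efficacy evaluation period) will be determined as follows". SAP 7.2 gives early withdrawal as its example of an incomplete period: "Subjects who do not have complete information for the efficacy evaluation period (for example, withdrew before 12 months".

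Test 17 refers to SAP 9.5.1, which adds no window of its own. It says the 18-month reduction "will be categorized and analyzed as described for the reduction in AF burden at 12 months (Section 9.4.1". SAP 9.4.1 defines its AAD subsets on the same period (for example "Subjects who have taken a Class I/III AAD during the efficacy evaluation period") and uses that period again for the repeat analysis in which AAD users count as failures.

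The only 18-month provision in SAP 7.4.2 concerns a date: the "18 month long-term follow-up visit date will be defined as necessary for efficacy purposes using the approach spelled out for the 12 month visit". SAP 13, on departures from the protocol, does not mention the matter.

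**The concern.** The outcome and the drug rule that qualifies it end at different times. A failure rule for new or increased AADs is there to keep drug-assisted burden reduction out of the success count. For that it has to cover the time up to the outcome reading. Here it stops about six months short.

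Two subjects with the same 18-month Holter result can therefore be scored in opposite ways purely by when the drug was started. The subset meant to hold subjects without a new AAD would, at 18 months, also include subjects who began one after the 12-month visit. The trial is open label, so late AAD starts could differ by arm, and the between-arm comparison would then carry that difference.

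**Working it through.** **1. Tracing the rule.** Test 17 (SAP 9.2) points to 9.5.1, which points to 9.4.1, which uses the efficacy evaluation period, which 7.4.2 ends at the 12-month visit. No step extends it to month 18. The wording fits tests 1, 12 and 13, whose outcomes are at 12 months. Tests 18 and 19, next to test 17, state their own 6-to-18-month windows, so the SAP does set 18-month windows elsewhere.

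**2. Length of the gap.** Inputs: 12-month visit at day 365 ± 30 and 18-month visit at day 550 ± 30 (protocol 6.6 and 6.7.1; SAP 3.2); default end of blanking at day 90 (SAP 7.4.2).

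- Nominal gap: 550 − 365 = 185 days.
- Shortest: (550 − 30) − (365 + 30) = 520 − 395 = 125 days.
- Longest: (550 + 30) − (365 − 30) = 580 − 335 = 245 days.
- Share of post-blanking time to month 18: 185 / (550 − 90) = 185 / 460 = 40%.

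**3. The plan's own figure.** The documents give no figure for test 17. The sample size in SAP 4 does reproduce: 40% vs 65%, two-sided 0.05, 80% power, 2:1, pooled variance without continuity correction gives 46 control and 92 treatment. Inflating by 10%, 46 × 1.10 = 50.6, rounded up to 51, and 51 × 3 = 153. The present point does not change it.

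**4. Effect on the comparison (illustration only).** Let *a* be an arm's 18-month success rate with the AAD check carried through month 18. Let *q* be the share of that arm that starts or increases an AAD after the 12-month visit, has no earlier failure and still meets the 90% cut. Then:

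- success rate as written = a + q
- difference as written = (a_T − a_C) + (q_T − q_C)

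Assumptions: *a* is 65% vs 40%, borrowed from the primary-endpoint design; 92:46 evaluable; the *q* values are invented, since the documents give none. Power is a normal approximation, whereas SAP 9.4.1 specifies Fisher's exact test.

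| q treatment / control | Rates as written | Difference | Approx. power |
|---|---|---|---|
| 0% / 0% | 65% vs 40% | 25 points | 80% |
| 10% / 10% | 75% vs 50% | 25 points | 83% |
| 5% / 15% | 70% vs 55% | 15 points | 42% |
| 15% / 5% | 80% vs 45% | 35 points | 99% |

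Equal shares raise both rates and leave the difference alone. Unequal shares move it towards the arm with more late starts.

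**The case against.** **The endpoint admits drug users.** Protocol 1.4.3 and 1.5.5, SAP 2.1.4 and 2.3.5, and the label of test 17 all describe 18-month burden reduction both on and off Class I/III AADs. On that reading a subject on an AAD begun at month 14 may properly be a success. This stands to the extent that the label and the failure rule in test 17 conflict, and any repair must deal with both. It does not rescue the 12-month cut-off. If AAD use is to be ignored, the rule should not be there; if it counts, the check should reach the outcome.

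**The period could be carried forward by analogy.** A programmer might read 9.5.1 and the 18-month date provision as moving the end of the period to month 18. That is possible, but the text moves a visit date and not the period, and SAP 7.2 and 7.4.2 both tie the period to 12 months. The literal reading is the stronger one.

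**Late AAD use is visible elsewhere.** Test 19 and SAP 9.5.5 count AAD therapy over 6 to 18 months, and Class I/III AADs have their own listing. A reader could find the affected subjects, but the coding of test 17 would be unchanged.

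**The stakes are low.** The endpoint is exploratory and is formally tested only if every earlier evaluable test is significant. This stands in full. SAP 9.5.1 does, however, call for the 18-month analysis in its own right, so the definition still shapes what is reported.

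**A stronger inference.** A reader might infer that the gap flatters the convergent procedure, or overstates its success by some set number of points. The documents do not support either. They give no rate of AAD starts between months 12 and 18 and no expected imbalance, and nothing shows that low burden in a late starter is due to the drug. More late starts in the control arm would work against the device.

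**Conclusion.** The point holds as an error in a stated rule: followed literally, test 17 and the AAD-dependent parts of 9.5.1 ignore new or increased AADs between the 12-month and 18-month visits. The length of the gap follows from the documents' own visit schedule. Its effect on results is unknown. Either arm's success rate can be raised, and the between-arm difference can be unchanged, too small or too large, depending on a late-start rate that the documents do not give.

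The importance is minor. The primary endpoint, its sample size, the safety analysis and the 12-month tests are untouched, as is the part of 9.5.1 that ignores AAD use for all subjects. The conclusion rests on reading the efficacy evaluation period as ending at the 12-month visit, which is the only end the SAP gives it.

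**What to change.** - In test 17 and SAP 9.5.1, for the version that counts new or increased AADs as failure, define the AAD window as the end of blanking through the 18-month visit. Use the same window for the AAD subsets carried over from 9.4.1.
- Report the 18-month version that ignores AAD use separately, as tests 1 and 3 separate the two versions at 12 months.
- Reword the label of test 17 so that it names the version tested in the sequence.

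Under the longer window, a subject who used a new AAD only before month 12 and was off it by month 18 remains a failure, as under the present rule. The SAP should say that this is intended.

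The cost is a few words in two sections and the matching programming. No new data are needed: protocol 6.7.1 already collects Class I/III AADs at the 18-month visit, and SAP 12 expects the 18-month outputs to cover concomitant medications. The change should be made before the 18-month data are analysed.

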9.3 Sensitivity Analyses

9.3.1 Sensitivity Analyses on Analysis Populations

The primary efficacy analysis will be repeated on the mITT and PP populations. If appropriate, Fisher's Exact test will be used in lieu of the chi-square test. The imputation methods described in Section 7.2 will be utilized for the analysis where appropriate.

9.3.2 Tipping-Point Analysis

A tipping-point analysis ^[3] will be conducted to explore the sensitivity of the results to the effect of missing data. To summarize, a tipping-point analysis evaluates the necessary difference in the number of events (for binary data) between treatment arms in the cohort of missing subjects at which the study conclusion is changed. For example, if each treatment arm had 20 subjects with missing data for treatment success/failure, a tipping-point analysis would start by assuming that 0/20 subjects in each treatment arm failed to achieve AF/AFL/AT freedom, and calculate the chi- square (or Fisher's Exact) test statistic. Then this would be repeated with 1, 2, 3 ... 20/20 subjects in one treatment arm, while the other treatment arm is held at 0/20 subjects. The second treatment arm is then increased to 1, 2, 3 ... 20/20 subjects (while the first arm is 0, 1 ... 20), so that every combination of number of failures among subjects with missing data across the two arms was compared. The "tipping point" is the point at which the p-value crosses the $\alpha=.05$ line. It is often summarized as "X more

treatment failures among the subjects with missing data in Arm A than those in Arm B" and can be displayed graphically as well. This information can then be used to evaluate the impact of the missingness, and how reasonable it might be for that pattern of data to have occurred if there were no missing data.

The tipping-point analysis will be performed on the primary efficacy analysis, using both the mITT and ITT populations (without the imputation method described in Section 7.2). The results will be displayed graphically, similar to Figure 1 of Yan, Li and Nan^[3].

9.3.3 **Geographical Differences**

The primary efficacy analysis may be repeated with pooled sites or regions as a covariate, to explore potential differences between geographic areas, using the ITT population.

9.3.4 **Multiple Imputation**

The primary efficacy analysis will be repeated on the ITT population, using multiple imputation to impute AF/AFL/AT freedom for subjects in who it was missing. Subjects who do not have complete information for the efficacy evaluation period, but have sufficient information to conclude that they would be classified as treatment failures, will be considered treatment failures and not imputed. The imputation will be limited to subjects in the ITT population.

The logistic regression method in SAS (version 9.3 or higher) will be used to impute AF/AFL/AT freedom, such as in the following pseudocode:

```
PROC MI data=xxx seed=xxxx out=xxx n impute=5;
  CLASS free ;
  FCS LOGISTIC (free = var1 var2 var3 var4) ;
  VAR var1 var2 var3 var4 free;
  run;
```

The covariates used may include the following. Other covariates may be specified as necessary:

- Demographic and baseline covariates
- Whether a 3 month visit was performed within window vs. not performed or performed out of window. An unscheduled visit falling within the window, which has sufficient information recorded for the ECG, Holter monitor, or rhythm disturbance evaluation to determine whether or not a subject is AF/AFL/AT free, will be treated as having the scheduled visit performed in window. (If all subjects in the ITT population have the visit performed within window, this covariate is not necessary).

- Whether the 6 month visit was performed within window vs. not performed or performed out of window. An unscheduled visit falling within the window, which has sufficient information recorded for the ECG, Holter monitor, or rhythm disturbance evaluation to determine whether or not a subject is AF/AFL/AT free, will be treated as having the scheduled visit performed in window. (If all subjects in the ITT population have the visit performed within window, this covariate is not necessary).
- AF burden (%) at baseline visit.
- SF-36 physical and mental health composite scores at baseline visit.
- AFSS composite score at baseline visit.
- Six-minute walk test distance walked (meters) at baseline visit.
- Total days of hospitalization in the 12 months prior to study procedure.
- Number of years in AF.
- Transdiaphragmatic vs sub-xiphoid access type.
- Left atrial size (at baseline) – to be dichotomized as per SAP section 6.3 if necessary.
- Left atrial volume (at baseline) – to be dichotomized as per SAP section 6.3 if necessary.
- Investigational site
- Geographic location - Europe, Region of United States (such as West, Southeast, Northeast, Central/Midwest) as per SAP section 9.3.3
- Persistent AF vs long standing persistent AF

From this list of covariates (and any other covariates included as necessary), the following shall be included as covariates in the imputation model, based on Section 2.2.1 of Berglund and Heeringa¹:

- Any demographic or baseline characteristics that are statistically significant between subjects with missing AF/AFL/AT freedom and subjects without that information missing (e.g., age, gender, ethnicity, race [white vs. non-white], height, weight, BMI, or smoking history) as described in Section 8.4 and presented in a summary table.
- Any demographic or baseline characteristics that are statistically significant between treatment arms as described in Section 8.4 and presented in a summary table.
- Any other covariate which is associated with AF/AFL/AT freedom, as determined by using Fisher's Exact test (for dichotomous covariates), Cochran-Mantel-Hanszel test

(for nominal or ordinal covariates), or Wilcoxon rank sum test (for continuous covariates), based on the subjects in the ITT population who are not being imputed.

- Any other covariate which is associated with a missing primary endpoint, as determined by using Fisher's Exact test (for dichotomous covariates), Cochran-Mantel-Hanszel test (for nominal or ordinal covariates), or Wilcoxon rank sum test (for continuous covariates), based on the subjects in the ITT population. That is, an indicator variable will be created to summarize whether a subject's AF/AFL/AT freedom is being imputed, and any covariate which is associated with that indicator variable will be retained.
- Any key analysis variables as determined by AtriCure (such as: left atrial size at baseline, number of years in AF, and geographic region)

If the resulting list of covariates results in an over-specified model or other statistical convergence issues, covariates will be removed until there is no longer a statistical issue. Covariates will be removed starting with obviously redundant variables (for example, height, weight, and BMI all being in the model) and then beginning with those which have the least relationship between the covariate and either the missingness indicator variables or AF/AFL/AT freedom. Key analysis variables will be retained throughout unless any of that group of covariates causes such issues, in which case they will be removed in an order discussed with the sponsor.

Five data imputation sets will be imputed using PROC MI as outlined above. The primary analysis will be performed separately for each of the imputation sets, and the results combined using PROC MIANALYZE. Those results will be presented in a summary table.

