4 SAMPLE SIZE CONSIDERATIONS

A sample size of 153 subjects is planned for this study, which is based on the primary endpoint of AF/AFL/AT freedom.

It is assumed that the success rate for the control arm (catheter ablation) is 40%,

and the study is designed to document superiority of EPi-Sense-AF with a 65% success rate. The sample size result, based on 2-sided $\alpha = .05$, 80% power, a 2:1 allocation of EPi-Sense-AF:catheter ablation, and a 10% drop out rate, is 102:51 or 153 subjects.

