If a subject exhibits AF, AFL, or AT or meets failure criteria, the subject will be classified as **not AF/AFL/AT free** for that time period. If a subject has insufficient efficacy assessments and does not meet failure criteria, and does not exhibit AF/AFL/AT on any efficacy assessments during that period, the subject will be classified as **indeterminate**, and subject to imputation as described in Sections 7.2 and 9.3. Further details on criteria for treatment failure are provided in study protocol section 1.5.

Does not exhibit AF, AFL, or AT is defined as:

- Has no atrial fibrillation, where atrial fibrillation is defined as a Holter monitor finding or ECG rhythm of 'AF' or 'Other' with description including atrial

fibrillation, where the Holter monitor date or ECG date falls within that period.

- Has no atrial flutter, where atrial flutter is defined as a Holter monitor finding or ECG rhythm of 'Typical AFL (Right Atrial)' or 'Atypical AFL (Left Atrial)' or 'Other' with description including atrial flutter, where the Holter monitor date or ECG date falls within that period.
- Has no atrial tachycardia, where atrial tachycardia is defined as a Holter monitor finding or ECG rhythm of 'AT' or 'Other' with description including atrial tachycardia, where the Holter monitor date or ECG date falls within that period.
- Has a Rhythm Disturbance Evaluation eCRF where 'any symptomatic AF/AFL/AT episodes' is marked No or Unknown at each visit where completed.
- Has a Holter monitor eCRF where the number of >30 second AF/AFL/AT episodes is 0 for each eCRF page where the Holter monitor date falls within that period.

A list of descriptions for 'Other' results from the Holter monitor and ECG will be tabulated and provided to the Medical Monitor or designee to determine whether the description is indicative of the subject having AF/AFL/AT. This tabulation will not include subject identifiers or treatment arm. Additional information collected on the Holter monitor, ECG, or Rhythm Disturbance Evaluation eCRF from that visit may also be provided to help with classification. This information will be finalized prior to database lock and subsequent unblinding of study sponsor, and incorporated into analysis datasets in order to determine if subjects meet criteria for to be AF/AFL/AT free at a given assessment, and hence determine if the subject is AF/AFL/AT free for a given period of time.

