9.1 Primary Efficacy Analysis

The binary primary endpoint of success or failure to achieve freedom from AF/AT/AFL absent class I and III AADs except for a previously failed or intolerant class I or III AAD with no increase in dosage following the 3 month blanking period through the 12 months post procedure follow-up visit will be compared between the two treatment groups using a chi-square test using a two-sided alpha of 0.05 to determine if superiority of the treatment arm is attained. This is detailed in Sections 2.3.1 and 7.4.5 of the SAP.

The analysis will be performed on the ITT population. If necessary, imputation will be performed as specified in Section 7.2.

Define P as the true percentage of subjects failing to achieve AF/AFL/AT freedom, where P_T is the true failure rate for the treatment arm and P_C for the control arm. The hypothesis to test is:

$$H_0: P_T = P_C \quad \text{vs} \quad H_a: P_T \neq P_C$$

The formula for the chi-square test is:

$$\chi^2 = \sum_{i=1}^n \frac{(O_i - E_i)^2}{E_i}$$

where O_i represents the number of observed events in the i^{th} cell and E_i represents the expected number of events in the i^{th} cell. H_0 is rejected in favor of H_a if the resulting p-value < 0.05 and the estimated P_T exceeds P_C . If $E_i < 5$ for any cell (that is, if the [number of subjects in a treatment arm * total number of successes / total number of subjects] is < 5 , or similarly for the number of failures), then the Fisher's Exact test will be used in lieu of the chi-square test.

If the $p \leq 0.05$, we will conclude that the percentages differ significantly between treatment arms.

The number and percent of subjects achieving AF/AFL/AT freedom will be summarized by treatment arm, and individual results listed by subject.

The primary efficacy analysis will be repeated on the specific subgroups as described in Section 6.3.

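### SAP 9.3.4: the multiple imputation makes no prespecified use of an arrhythmia-free month-6 result, so imputed success is too low for subjects known to be free at month 6

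*SAP*

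**What the plan says.** SAP 9.3.4 repeats the primary analysis on the ITT population "using multiple imputation to impute AF/AFL/AT freedom for subjects in who it was missing". The method is stated as follows: "The logistic regression method in SAS (version 9.3 or higher) will be used to impute AF/AFL/AT freedom". The pseudocode has a single outcome variable, and five imputed data sets are analysed and pooled.

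The named candidate covariates are demographic and baseline items (AF burden at baseline only), access type, site, region, AF classification, and two flags for whether the month-3 and month-6 visits were performed in window. The SAP says that other covariates may be added. It keeps those associated with outcome or with missingness, plus key variables chosen by the sponsor; the examples given are left atrial size at baseline, years in AF and region. Covariates are removed if the model is over-specified or does not converge. Treatment arm is not named.

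SAP 7.4.5 requires arrhythmia-free evidence at both month 6 and month 12 for success. A subject with too few assessments who meets no failure criterion and "does not exhibit AF/AFL/AT on any efficacy assessments during that period, the subject will be classified as" indeterminate goes to imputation. By contrast, SAP 9.3.4 says that subjects with incomplete data who "have sufficient information to conclude that they would be classified as treatment failures, will be considered treatment failures and not imputed".

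**The concern.** The two kinds of partial evidence are handled differently. A recurrence at month 6 settles the outcome. A documented absence of recurrence at month 6, with month 12 missing, leaves the whole-period outcome to be imputed, and no named predictor carries the month-6 finding.

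Every imputed subject with a usable month-6 result is therefore arrhythmia-free at that visit. The subjects used to fit the model include those who failed by month 6. The model applies a success rate that still counts early failures to people known not to be early failures, so the imputed probability is too low.

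The primary rule in SAP 7.2 already imputes failure, and the tipping-point analysis scans combinations without estimating which are plausible. Multiple imputation is the one planned analysis that estimates the missing outcomes from data, so it should not share the downward bias of the failure rule.

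**Working it through.** **Planning figures.** SAP section 4 takes 40% as the success rate under catheter ablation alone. For the device it says that "the study is designed to document superiority of EPi-Sense-AF with a 65% success rate". The design is "80% power, a 2:1 allocation of EPi-Sense-AF:catheter ablation, and a 10% drop out rate, is 102:51 or 153 subjects". SAP 9.1 tests "using a two-sided alpha of 0.05 to determine if superiority of the treatment arm is attained".

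**Reproducing the sample size.** Pooled-variance formula, no continuity correction, r = 2, weighted mean rate (0.40 + 2 × 0.65)/3 = 0.5667:

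n(control) = [1.960 × √(1.5 × 0.5667 × 0.4333) + 0.842 × √(0.40 × 0.60 + 0.65 × 0.35/2)]² / 0.25² = 45.7, so 46.

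Total 46 + 92 = 138, and 138/0.9 = 153.3, against 153 stated. The figure reproduces.

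**Assumptions for the imputation.** The SAP gives no figure here, and neither document says when failures occur. Let p be the planned success rate, s the share of failures seen by month 6, and m the share of an arm free at month 6 with month 12 missing. Missingness is at random given the month-6 result, and arm is in the model unless stated.

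**Step 1: what a subject free at month 6 should receive.** P(success | free at 6) = p / [p + (1 − p)(1 − s)]. At s = 0.5:
- control 0.40/0.70 = 0.571
- convergent 0.65/0.825 = 0.788

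**Step 2: what the named model gives.** If it simply returned the planned rates, 0.40 and 0.65. Among subjects whose outcome is known, the rate is p(1 − m/q)/(1 − m), with q = p + (1 − p)(1 − s). At s = 0.5, m = 0.10:
- control 0.40 × (1 − 0.10/0.70)/0.90 = 0.381
- convergent 0.65 × (1 − 0.10/0.825)/0.90 = 0.635

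**Step 3: effect on the arms.** With m = 0.10 in each arm (the SAP's dropout rate):

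| s | Should be: control, convergent | Named model: control, convergent | Estimated difference (true 25.0) |
|---|---|---|---|
| 0.3 | 0.488, 0.726 | 0.390, 0.642 | 25.1 |
| 0.5 | 0.571, 0.788 | 0.381, 0.635 | 25.4 |
| 0.7 | 0.690, 0.861 | 0.368, 0.627 | 25.9 |

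The estimated arm rates equal the named-model values: control 36.8-39.0% against 40%, convergent 62.7-64.2% against 65%.

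**Step 4: unequal missingness, s = 0.5, draws of 0.40 and 0.65.** The splits are illustrative.
- 5% convergent, 15% control: 0.15 × 0.171 − 0.05 × 0.138 = 0.019, difference overstated by 1.9 points. With the Step 2 formula for known outcomes (0.370 and 0.643): 0.15 × 0.202 − 0.05 × 0.145 = 0.023.
- 15% convergent, 5% control: 0.15 × 0.138 − 0.05 × 0.171 = 0.012, difference understated by 1.2 points.

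**Step 5: arm left out.** With 10% missing per arm, both arms receive the same draw and the difference shrinks to 22.6-23.3 points over s = 0.3-0.7. In the 5%/15% case, a pooled draw of (2 × 0.65 + 0.40)/3 = 0.567 understates convergent by 0.05 × (0.788 − 0.567) = 1.1 points and control by 0.15 × (0.571 − 0.567) = 0.1, so the difference is understated by about 1.0 point.

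**Step 6: the attendance flag.** Success needs month-6 evidence, so a subject with a known outcome but no month-6 evidence can only be a failure. In 4,000 simulated trials (102:51, s = 0.5, 5% missing month 6, 10% missing month 12), 95% had such subjects, and in every one of those trials all of them were failures. Among attenders the model gave 0.389 and 0.637, against 0.573 and 0.787 when fitted on those free at month 6. The flag separates attenders from non-attenders but does not correct the attenders' probability.

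**The case against.** Four points can be made for the plan.

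**Observed results are not all discarded.** A reader might infer that the imputation ignores rhythm data. It does not: documented failures are kept as failures. Only arrhythmia-free partial results go unused.

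**A subject free at month 6 need not be imputed like one never assessed.** That stronger reading is tempting, but month-6 attendance is a candidate covariate and enters if associated with outcome or missingness. With the flag in the model the two groups are imputed very differently. The reading would hold only if the flag were not selected, or were removed under the convergence rule.

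**The covariate list is open.** This also stands: the SAP does not exclude month-6 status, it fails to prespecify it. Adding it to the one-step model is not a clean cure, however. Month-6 failure determines overall failure, so the variable produces separation. The convergence rule removes weaker covariates first, but the problem would persist until this one went too.

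**Little depends on it.** The primary analysis imputes failure, and the tipping-point analysis covers every combination of missing outcomes in both arms. A reader might also infer a tilt towards the device. That needs both more control dropout and arm in the model. The documents give a single 10% dropout rate and do not name arm, and reversing the dropout pattern or omitting arm reverses the sign.

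**Conclusion.** The point holds as a minor weakness in one sensitivity analysis. For subjects known to be free at month 6, the named model understates the chance of success. With half of failures by month 6 and arm in the model, it gives about 0.38-0.40 instead of 0.57 in control and 0.64-0.65 instead of 0.79 in convergent. These are per-subject probabilities. At trial level, with 10% missing per arm and 30-70% of failures by month 6, each arm's rate is understated by roughly 1-3 points and the difference moves by 0.1-0.9 points. Unequal dropout can put the difference out by about 1-2 points in either direction. Omitting treatment arm shrinks it to 22.6-23.3 points against 25, a larger effect than the missing month-6 result has under equal dropout.

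All of this rests on the planned success rates, an assumed timing of failures, and missingness at random given the month-6 result. The primary failure imputation and the tipping-point analysis are unchanged, and nothing here puts the primary conclusion in doubt.

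**What to change.** Amend SAP 9.3.4 to impute in sequence:

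1. Define Y6 (free from the end of blanking through month 6) and Y12 (free from month 6 through month 12).
2. Keep every observed value and every known failure.
3. Impute missing Y6.
4. Impute missing Y12 among subjects with Y6 = free, so that the Y12 model is fitted only on such subjects.
5. Require treatment arm in both models, with the selected baseline covariates.
6. Count success only if both are free, then analyse and pool as planned.

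One limit should be stated in the text: if month 6 is missing and month 12 is arrhythmia-free, Y12 is kept and only Y6 is imputed, without help from the later result.

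The cost is a few lines of SAP text and some programming, with two imputation models instead of one. The month-6 and month-12 rhythm data are already scheduled, and the endpoint, the primary test and the burden on subjects do not change.
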